10.11 Secondary Efficacy Analyses

The secondary efficacy variables will be summarized at Days 4, 8, and 21 for absence of anterior chamber cells and at Days 8, 15 and 21 for absence of ocular pain, similarly to the primary efficacy summaries. Additionally, anterior chamber cell grade and ocular pain score at each visit and change from baseline will be summarized using continuous and discrete summary statistics.

Absence of anterior chamber flare and anterior chamber flare grade and the sum of anterior chamber cell and flare grade, including absence of both anterior chamber cell and flare will be summarized similarly to anterior chamber cells and pain at each visit.

10.12 Safety Analyses

The primary safety analysis will summarize ocular treatment-emergent AEs (TEAEs) in the study eye for all treated patients using discrete summaries at the patient- and event-level by system organ class and preferred term for each treatment group. A TEAE will be defined as occurring on or after the day that treatment is initiated. An additional analysis will investigate ocular AEs for the non-study eye. Non-ocular TEAEs will be summarized using discrete summaries at the patient- and event-level by system organ class and preferred term for each treatment group. Treatment-related ocular and non-ocular TEAEs will be summarized similarly. Ocular and non-ocular TEAEs will also be summarized by severity.

The IOP data will be summarized at each visit using both continuous summaries (including change from baseline) and discrete summaries (including the proportion of patients with change in IOP from baseline ≥ 10 mm Hg and the proportion of patients with an IOP ≥ 30 mm Hg that occurs at any time following instillation of study treatment) as well as shift tables.

Slit lamp biomicroscopy and dilated indirect ophthalmoscopic examination measures will be summarized at each visit using discrete summary statistics.

Visual acuity data will be summarized at each visit, using discrete summaries, including change from baseline in the number of lines and the proportion of patients with change from previous visit of ≥ 2 lines.

10.13 Subgroup Analysis

No subgroup analyses are planned.

10.14 Interim Analysis

No interim analyses are planned.

11 COMPLIANCE WITH GOOD CLINICAL PRACTICES, ETHICAL CONSIDERATIONS, AND ADMINISTRATIVE ISSUES

This study will be conducted in compliance with the protocol, Good Clinical Practices (GCPs), including the International Conference on Harmonization (ICH) Guidelines, and in general, consistent with the Declaration of Helsinki. In addition, all applicable local, state, and federal requirements relevant to the use of study drugs in the countries involved will be adhered to.

11.1 Protection of Human Subjects

11.1.1 Patient Informed Consent

Informed consent must take place before any study specific procedures are initiated. Signed and dated written informed consent must be obtained from each patient and/or from the patient's parent or legal guardian prior to enrollment into the study. If the patient is under the legal age of consent, the consent form must be signed by a legal guardian or as required by state and/or local laws and regulations.

All informed consent forms must be approved for use by the Sponsor and receive approval/favorable opinion from an IRB/IEC prior to their use. If the consent form requires revision (e.g., due to a protocol amendment or significant new safety information), it is the Investigator's responsibility to ensure that the amended informed consent is reviewed and approved by Sponsor prior to submission to the governing IRB/IEC and that it is read, signed and dated by all patients subsequently enrolled in the study as well as those currently enrolled in the study.

If informed consent is taken under special circumstances (oral informed consent), then the procedures to be followed must be determined by CRO and study Sponsor and provided in writing by CRO and study Sponsor prior to the consent process.

11.1.2 Institutional Review Board (IRB) Approval

This study is to be conducted in accordance with Institutional Review Board regulations (U.S. 21 CFR Part 56.103). The Investigator must obtain appropriate IRB approval before initiating the study and re-approval at least annually.

Only an IRB/ERC approved version of the informed consent form will be used.

11.2 Ethical Conduct of the Study

This study will be conducted in accordance with the ethical principles that originated with the Declaration of Helsinki.

11.3 Patient Confidentiality

All personal study patient data collected and processed for the purposes of this study should be maintained by the Investigator and his/her staff with adequate precautions as to ensure that the confidentiality of the data in accordance with local, state, and federal laws and regulations.

Monitors, auditors and other authorized representatives of CRO, the Sponsor, the IRB/IEC approving this study, the FDA, the DHHS, other domestic government agencies, and other foreign regulatory agencies will be granted direct access to the study patient's original medical and study records for verification of the data and/or clinical trial procedures. Access to this information will be permitted to the aforementioned individuals to the extent permitted by law.

A report of the results of this study may be published or sent to the appropriate health authorities in any country in which the study drug may ultimately be marketed, but the patient's identity will not be disclosed in these documents.

11.4 Documentation

Source documents may include a patient's medical records, hospital charts, clinic charts, the Investigator's study patient files, as well as the results of diagnostic tests such as X-rays, laboratory tests, and ECGs. The Investigator's copy of the CRFs serves as the Investigator's record of a patient's study-related data.

11.4.1 Retention of Documentation

All study related correspondence, patient records, consent forms, record of the distribution and use of all study drug and copies of CRFs should be maintained on file for at least two years after the last approval of a marketing application in an ICH region and until there are no pending or contemplated marketing applications in an ICH region; or until at least two years have elapsed since the formal discontinuation of clinical development of the investigational product. These documents will be retained for a longer period if required by the applicable regulatory requirements or by an agreement with the Sponsor. It is the responsibility of the Sponsor to inform the Investigator/institution as to when these documents no longer need to be retained.

If the responsible Investigator retires, relocates, or for other reasons withdraws from the responsibility of keeping study records, custody must be transferred to a person who will accept the responsibility. The Sponsor must be notified in writing of the name and address of the new custodian.

11.5 Labeling, Packaging, Storage, Accountability, and Return or Disposal of Study Drug

11.5.1 Labeling/Packaging

Each study drug kit will be labeled with a 5-digit study drug kit number and will contain one bottle of study drug. All bottles of active and placebo treatment will be identical in appearance and will be packaged in identical containers. The study drug kit and each bottle will have a label bearing information meeting applicable regulatory requirements. Study drug bottles will come with directions for use and other appropriate information on each part. Study drug will be packaged and labeled based on the randomization list generated prior to the start of the study.

11.5.2 Storage of Study Drug

The study drug product must be stored upright at 2° to 8°C (36° to 46° F), in a refrigerator, protected from freezing, protected from strong light, and stored in a secure area accessible only to the Investigator and his/her designees. The study drug product will be administered only to patients entered into the clinical study, in accordance with the conditions specified in this protocol.

11.5.3 Accountability of Study Drug

The study drug is to only be prescribed by the Principal Investigator or his/her named sub-Investigator(s), and is to only be used in accordance with this protocol. The study drug must only be distributed to patients properly qualified under this protocol to receive study drug.

The Investigator must keep an accurate accounting of the study drug received from the supplier. This includes the amount of study drug dispensed to patients, amount of study drug returned to the Investigator by the patients, and the amount returned or disposed upon the completion of the study. A detailed inventory must be completed for the study drug.

11.5.4 Return or Disposal of Study Drug

All study drug will be returned to the Sponsor or their designee or destroyed at the study site. The return or disposal of study drug will be specified in writing.

11.6 Recording of Data on Source Documents and eCRFs

The Investigator is responsible for ensuring that study data is completely and accurately recorded on each patient's eCRF, source document, and all study-related material. All study data should also be attributable, legible, contemporaneous, and original. Recorded datum should only be corrected in a manner that does not obliterate, destroy, or render illegible the previous entry (e.g., by drawing a single line through the incorrect entry and writing the revision next to the corrected data). An individual who has corrected a data entry should make clear who made the

correction and when, by adding to the correction his/her initials as well as the date of the correction.

11.7 Handling of Biological Specimens

Not applicable.

11.8 Publications

Authorship and manuscript composition will reflect cooperation among all parties involved in the study. Authorship will be established before writing the manuscript. The Sponsor will have the final decision regarding the manuscript and publication.

APPENDIX 1: EXAMINATION PROCEDURES

OCULAR PAIN GRADING SCALE (STUDY EYE)

Ocular Pain will be assessed by the patient at screening and at each follow-up visit, utilizing a Numerical Pain Rating Scale¹ graded from 0 to 10. Patients will assess the level of pain they are experiencing in the study eye at the time of the assessment. Patients may only select whole numbers on the scale.

The examiner will ask the patient the following question related to Figure 1:On a scale of 0 to 10, in which 0 is no pain and 10 is the worst possible or unbearable pain, please mark on the scale the whole number that best describes the pain or discomfort you are feeling in the operated eye at this time. The middle of the scale (around 5) can be used to describe "moderate pain".

Figure 1Ocular Pain Grading Scale

At the screening assessment visit, the patient will be asked about the eye scheduled for surgery.

The examiner will record the number selected by the patient on the appropriate eCRF.

¹ Reference 4. National Institutes of Health (NIH). Numeric Pain Rating Scale (NPRS). . Warren Grant Magnuson Clinical Center. Pain Intensity Instruments. July 2003.

PIN-HOLE VISUAL ACUITY PROCEDURES (EACH EYE)

Pin-hole, LogMAR visual acuity must be assessed using an ETDRS chart. The procedure used will be consistent with the recommendations provided for using the ETDRS eye chart. Pin-hole visual acuity should be evaluated at the beginning of each visit in the study (i.e., prior to slit lamp examination). Pin-hole visual acuity testing should be done with a pin-hole occluder.

Equipment

The visual acuity chart to be used is the ETDRS chart. If smaller reproduction (18" by 18", e.g., from Prevent Blindness) wall charts are used, the patient viewing distance should be exactly 10 feet (or as specified by the manufacturer). In ALL cases, for purposes of standardizing the testing conditions during the study, all sites must use only the 'R' charts, and the right eye should be tested first. For reflectance (wall) charts, the chart should be placed frontally and well-illuminated.

Measurement Technique

The chart should be at a comfortable viewing angle. A pin-hole occluder should be applied to the right eye which should be tested first. The patient should attempt to read each letter, line-by-line, left to right, beginning with line 1 at the top of the chart. The patient should be told that the chart has letters only, no numbers. If the patient reads a number, he or she should be reminded that the chart contains no numbers, and the examiner should then request a letter in lieu of the number.

The patient should be asked to read slowly, so as to achieve the best identification of each letter. He/she is not to proceed to the next letter until he/she has given a definite response.

If the patient changes a response (e.g., "that was a 'C' not an 'O'") before he has read aloud the next letter, then the change must be accepted. If the patient changes a response having read the next letter, then the change is not accepted. The examiner should never point to the chart or to specific letters on the chart during the test.

A maximum effort should be made to identify each letter on the chart. When the patient says he or she cannot read a letter, he or she should be encouraged to guess. If the patient identifies a letter as one of two letters, he or she should be asked to choose one letter and, if necessary, to guess. When it becomes evident that no further meaningful readings can be made, despite encouragement to read or guess, the examiner should stop the test for that eye. However, all letters on the last line should be attempted as letter difficulties vary and the last may be the only one read correctly. The number of letters missed or read incorrectly should be noted.

PIN-HOLE VISUAL ACUITY PROCEDURES (cont.)

LogMAR Visual Acuity Calculations

The last line in which a letter is read correctly will be taken as the base logMAR reading. To this value will be added the number "N x 0.02" where 'N' represents the total number of letters missed up to and included in the last line read. This total sum represents the logMAR visual acuity for that eye.

For example: Patient correctly reads 4 of 5 letters on the 0.2 line, and 2 of 5 letters on the 0.1 line.

Base LogMAR	= 0.1
N (total number of letters incorrect on line 0.2 as well as 0.1)	
	= 4
N x T (T=0.02)	= 0.08
Base \log MAR + (N x T)	= 0.1 + 0.08
logMAR VA	= 0.18

Repeat the procedure for the left eye.

In order to provide standardized and well-controlled assessments of visual acuity during the study, all visual acuity assessments at a single site must be consistently done using the same lighting conditions and pin-hole during the entire study. If the same conditions and use of pin-hole cannot be used, the reason for the change in condition and pin hole should be documented.

SLIT LAMP BIOMICROSCOPY (EACH EYE):

Slit lamp biomicroscopy will be performed during the study. Observations will be graded as Normal or Abnormal. All abnormal findings, other than the endpoints being assessed by the study scales (anterior chamber cells and flare), will be documented on each patient's source document and corresponding electronic case report form (eCRF). All abnormal findings will be categorized as clinically significant (findings that may interfere with study parameters or otherwise confound the data as determined by the investigator) and not clinically significant.

The following will be examined at each visit:

- Eyelid
- Conjunctiva
- Cornea
- Iris
- Lens
- Anterior chamber

External examination and biomicroscopy will be performed using a slit lamp. Magnification will be consistent with standard clinical practice. The patient will be seated.

DURING SLIT-LAMP BIOMICROSCOPY: ANTERIOR CHAMBER CELLS AND FLARE (STUDY EYE)

The slit beam observations should be assessed in a dark room using a slit beam of 1.0 mm height and 1.0 mm width with maximum luminance, with 16x magnification, 1x1mm oblique high intensity beam fluorescein dye is to be instilled into the ocular cul-de-sac, or alternatively, fluorescein strips may be used to facilitate this examination.

Anterior Chamber Cells and Flare

The anterior chamber cell count will be recorded as the actual number of cells observed if fewer than 10 cells are seen (only white blood cells should be counted; red blood cells and pigment cells should not be counted). Flare will be graded using the SUN* Working Group grading scheme.

Anterior Chamber Cells			
Grade Number of Cells in Field			
0	0 cells		
1	1 to 10 cells		
2	11 to 20 cells		
3	21 to 50 cells		
4	> 50 cells		

Flare		
Grade Description		
0	None	
1+	Faint	
2+	Moderate iris and lens details clear	
3+	Marked iris and lens details hazy	
4+	Intense fibrin or plastic aqueous	

*Reference 3. Standardization of the Uveitis Nomenclature (SUN): Jabs et al. 2005.

INTRAOCULAR PRESSURE (IOP) PROCEDURES (EACH EYE)

Applanation tonometry, Goldmann tonometer required. Do NOT use non-contact tonometry.

DILATED INDIRECT OPHTHALMOSCOPIC EXAMINATION (EACH EYE)

Dilated indirect ophthalmoscopic examination will be performed as indicated in the study flowchart in Appendix 2 after the patient ICF/authorization, medical history/demographics, urine pregnancy test (if applicable), pin-hole visual acuity, slit lamp biomicroscopy, and tonometry. The examination will not be performed until the patient's eyes are deemed sufficiently dilated in the opinion of the investigator. The investigator will note any findings present and whether or not the findings are clinically significant or not clinically significant. Findings which are clinically significant will be described.

The following will be examined:

- Vitreous
- Retina
- Macula
- Choroid
- Optic Nerve

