4 OVERALL STUDY DESIGN

This trial will be a multi-center, double-masked, randomized, dose-ranging, placebocontrolled study consisting of 6 visits over approximately 7 weeks (49 days). Randomization will be used to avoid bias in the assignment of patients to treatment, to increase the likelihood that known and unknown patient attributes (e.g., demographics and baseline characteristics) are evenly balanced across treatment groups, and to enhance the validity of statistical comparisons across treatment groups. Masked treatment will be used to reduce potential of bias during data collection and evaluation of clinical endpoints.

At Visit 1 (Day -1 to Day -28), patients will be screened to ensure that they meet all initial inclusion criteria and none of the exclusion criteria. Medical and medication histories will be taken, the patients will subjectively grade ocular pain using the scales provided, and pin-hole visual acuity will be assessed. The Investigator will then perform a slit lamp biomicroscopic examination with intraocular pressure (IOP) measurement, and grading of anterior chamber inflammation. A dilated indirect ophthalmoscopic examination will also be performed. Female patients of childbearing potential will be given a urine pregnancy test.

At Visit 2 (Day 1, 24 ± 6 hours post-surgery), patients' medical and medication histories will be updated, patients will be queried for ocular pain, pin-hole visual acuity will be assessed, and the Investigator will perform a slit lamp biomicroscopic evaluation, IOP

measurement, and grading of anterior chamber inflammation. Qualifying patients will then be randomized to one of the following treatment groups (in a 1:1:1 ratio): RTA 408 Ophthalmic Suspension 0.5% (N=35), RTA 408 Ophthalmic Suspension 1.0% (N=35), or placebo for RTA 408 Ophthalmic Suspension (N=35). Study drug will be dispensed along with the Study Drug Compliance Diary. A trained unmasked technician will instruct patients on how to instill the study drug twice daily in the morning and evening (approximately 12 hours apart) for 14 days on the eye that underwent surgery. The first dose of study drug will be instilled in-office.

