15.4 Pin-Hole Visual Acuity (ETDRS)

The logarithm of the minimum angle of resolution (logMAR) pin-hole visual acuity is assessed at each visit using an EDTRS chart. Pin-hole visual acuity should be done with a pin-hole occluder.

The observed and change from baseline pin-hole visual acuity will be summarized for each eye (study eye and non-study eye) using descriptive statistics (number of observations, mean, standard deviation (SD), median, minimum, and maximum values) by visit for each treatment group and for all patients combined. In addition, the proportion of patients with a worsening (increase) in their logMAR pin-hole visual acuity from the previous visit of ≥2 lines will be presented using frequency counts and percentages. A patient listing of pin-hole visual acuity will also be produced.

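### On the natural reading of Appendix 1, a left study eye is tested on letters the fellow eye has just read aloud, so recall can hide an acuity loss near the two-line safety flag

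*Protocol*

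**What the plan says.** The pin-hole acuity procedure in Protocol Appendix 1 sets one chart type for every case, for the stated purpose of standardizing test conditions: "all sites must use only the 'R' charts, and the right eye should be tested first". The measurement technique repeats the order ("A pin-hole occluder should be applied to the right eye which should be tested first") and the scoring section closes with "Repeat the procedure for the left eye". Neither place calls for a change of chart between eyes.

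On letters the patient cannot see, the instruction is: "When the patient says he or she cannot read a letter, he or she should be encouraged to guess". The score is the base logMAR of the last line on which a letter is read correctly, plus 0.02 for each letter missed up to and including that line.

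Acuity is measured in each eye at all six visits (Appendix 1 and Appendix 2). It is listed as a safety measure in Protocol 6.2 and SAP 3.3. SAP 15.4 summarises observed values and change from baseline for each eye, and sets one threshold: "the proportion of patients with a worsening (increase) in their logMAR pin-hole visual acuity from the previous visit of ≥2 lines".

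**The concern.** Inclusion criterion 4 requires unilateral surgery but does not restrict the side, so the study eye may be the left. That eye is then always second, minutes after the fellow eye has read what appear to be the same letters aloud. A patient who is encouraged to guess can supply a remembered letter, and the scoring rule credits it like a letter seen.

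The error runs in the reassuring direction. It applies when the study eye has newly lost letters that the fellow eye still reads, which is the event the two-line flag is meant to catch. The synopsis describes this as the first clinical study of the ophthalmic suspension, so the sensitivity of a named safety measure has some value. Randomization should balance the effect across arms but does not restore sensitivity: if the same share of true losses goes unflagged in each arm, the difference in flagged counts shrinks too.

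**Working it through.** **Inputs from the documents:** 0.02 logMAR per letter and 5 letters per line (Appendix 1 scoring rule and example); flag at a worsening of 2 lines or more from the previous visit (SAP 15.4); 105 patients (Protocol 5.1).

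**Assumed, because the documents give no figure:** the probability *q* that a lost letter is recalled, and the share of study eyes that are left eyes.

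**1. Reproduce the protocol's example.** 4 of 5 letters read on the 0.2 line and 2 of 5 on the 0.1 line. Letters missed: N = 1 + 3 = 4. Score = 0.1 + 4 × 0.02 = 0.18, which matches.

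**2. Value of one recalled letter.** On a line already counted, one more correct letter lowers N by 1, so the score improves by 0.02. If it is the only letter correct on the next line down, the base falls by 0.10 and four misses add 4 × 0.02 = 0.08, again a net gain of 0.02.

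**3. The flag in letters.** 2 lines × 5 letters × 0.02 = 0.20 logMAR, or 10 letters.

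**4. Recall needed to miss the flag.** Let L be the true loss in letters, and r0 and r1 the letters credited through recall at the previous and current visits. Recorded loss = 0.02 × (L − (r1 − r0)), so only the excess of recall over the previous visit counts. The flag is missed when r1 − r0 is at least L − 9:

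| True loss L | Excess recalled letters needed | Recorded loss |
|---|---|---|
| 10 (0.20) | 1 | 0.18 |
| 12 (0.24) | 3 | 0.18 |
| 15 (0.30) | 6 | 0.18 |
| 20 (0.40) | 11 | 0.18 |

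**5. Chance that the flag is missed.** Suppose that the fellow eye can read every newly lost letter, that each is recalled independently with probability *q*, and that recall of letters unseen at both visits is nil or equal at the two visits. The excess X is then Binomial(L, *q*), and P(missed) = P(X ≥ L − 9). For L = 10 and *q* = 0.05 this is 1 − 0.95^10 = 0.401. In full:

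| *q* | L = 10 | L = 12 | L = 15 | L = 20 |
|---|---|---|---|---|
| 0.05 | 0.401 | 0.020 | 0.000 | 0.000 |
| 0.10 | 0.651 | 0.111 | 0.002 | 0.000 |
| 0.20 | 0.893 | 0.442 | 0.061 | 0.001 |
| 0.30 | 0.972 | 0.747 | 0.278 | 0.017 |
| 0.50 | 0.999 | 0.981 | 0.849 | 0.412 |

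**6. Patients exposed.** If 40% to 60% of study eyes are left eyes, 0.40 × 105 = 42 to 0.60 × 105 = 63 patients have a study eye that is always tested second. These are patients exposed to the sequence, not measurements shown to be biased.

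**7. With a different letter set for the left eye,** the fellow eye's reading at that visit supplies no letters to recall, so *q* for this source is 0. A true loss of 10 letters or more then scores at least 0.20 and is flagged, apart from ordinary measurement error.

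**The case against.** The strongest reply is that using one chart type is a deliberate choice with a stated reason, and that the shared letter set is itself an inference. The documents do not define 'R', they use the plural, and the appendix adds that "The procedure used will be consistent with the recommendations provided for using the ETDRS eye chart" without reproducing those recommendations. This stands as a limit on certainty. Yet the rule covers every case and allows only one chart type, and no section gives the second eye other letters. If different letters were intended, the text needs a sentence saying so.

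The arithmetic can also be called fragile: a loss exactly at a threshold falls below it with one letter gained from any source, including ordinary test-retest variation. That is true, and it is why the result is confined to losses near two lines. Two further limits stand. The fellow eye may read fewer lines than the operated eye, which leaves less to recall. And recall present at both visits cancels, so only credit for newly lost letters matters.

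A reader might infer that the trial as a whole would under-detect vision loss. The documents do not support that. SAP 15.4 also reports observed acuity, change from baseline and patient listings. These rest on the same readings but not on the threshold. Independently of the chart, slit lamp and IOP examinations take place at every visit, a dilated examination at screening and exit, and adverse event queries from Visit 2 onward. Protocol 9.2 has an explicit note on visual threat.

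A reader might also infer that the distortion grows with each visit, since the patient reads the chart 2 eyes × 6 visits = 12 times. Repetition makes some learning possible in either eye, but nothing in the documents shows that it accumulates or by how much.

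**Conclusion.** The point holds as a minor, specific weakness in a measurement procedure. As written, a left study eye is naturally read as being tested on letters just read by the fellow eye, and recalled letters can hide a loss near the two-line flag. At an assumed 5% to 20% recall per lost letter, a 10-letter loss is missed about 40% to 89% of the time and a 12-letter loss about 2% to 44%. A 15-letter loss is missed at most about 6% of the time and a 20-letter loss almost never; hiding those would take heavier recall.

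These figures rest on one letter set for both eyes, independent recall, and a fellow eye that can read all the lost letters. No document supplies a recall rate, so they show sensitivity to an assumption and do not estimate what would happen. Acuity is a descriptive safety variable for which no between-arm test is planned. No conclusion on anterior chamber cells or pain depends on it.

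**What to change.** In the equipment paragraph of the acuity procedure in Appendix 1, replace the 'R'-only rule with one named, fixed ETDRS letter chart for the right eye and a different named, fixed one for the left eye, the same pair at every site and visit. The closing instruction for the left eye should refer to its own chart. Eye order, scoring rule and SAP 15.4 can stay as they are, and testing remains just as standardized.

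The cost is about one sentence and one additional chart at sites that hold only the 'R' chart. The fix removes same-visit carry-over between eyes. It does not remove learning across visits, because each eye still meets its own chart six times.
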